3. INVESTIGATION PLAN

3.1 STUDY DESIGN

This is a single-center, randomized, controlled, open-label, crossover study to investigate the nicotine PK profiles of variants of P4M3 Gen 2.0, an electronic nicotine delivery system (ENDS), compared to cigarettes. In addition, PD effects (subjective effects and related behavioral assessments) will be evaluated to provide further insights on product evaluation. The study will be conducted with 3 periods and 6 sequences in a cross-over design.

A Screening Visit will be conducted within 28 days (Day -29 to Day -2) prior to Admission (Day -1) to the investigational site (Figure 1). The investigational site staff will do a demonstration of P4M3 Gen 2.0, without product use, during the Screening Visit.

Figure 1 Study Design

Abbreviations: CM35 = P4M3 Gen 2.0 Classic Menthol 3.5% nicotine; CA35 = P4M3 Gen 2.0 Classic Auburn 3.5% nicotine; Cig= Subjects' own cigarette smoking; P4M3 = Electronic Nicotine Delivery System P4M3 Gen 2.0

Qualified subjects will return to the investigational site for Day -1. Subjects should have fasted for at least 10 hours prior to the safety laboratory assessments. After confirmation of eligibility, subjects will be enrolled. All subjects that are not enrolled will be considered as screen failures.

Philip Morris Products S.A.
P4M3 Gen 2.0, P4-PK-04-US

██████████ Statistical Analysis Plan Number CA34617

On Day -1, enrolled subjects will perform a product test using P4M3 Gen 2.0 Classic Auburn 3.5% (CA35) variant *ad libitum* for up to 10 minutes. After the product test, subjects not willing and/or not ready to use P4M3 Gen 2.0 during the study will be discontinued from the study, will enter the 3-day Safety Follow-up and will be replaced.

Subjects willing and ready to use 2 variants of P4M3 Gen 2.0 during the study after product test will start their confinement period of 3 days. The brand of subjects' cigarettes will be recorded.

Thirty-six (36) subjects will be randomized to 1 of 6 possible sequences of product use on Day 1 to Day 3 (see Figure 1). On Day 1 to Day 3, after at least 12 hours of abstinence from any nicotine/tobacco containing products (nicotine wash-out), subjects will smoke a cigarette or use a variant of P4M3 according to randomized product use sequence *ad libitum* for 6 minutes (\pm 30 seconds). The weight of each P4M3 Gen 2.0 Cartridge will be determined before and after product use to estimate the amount of nicotine delivered in the aerosol during the 6-minute *ad libitum* use period. Subjects will use a variant of P4M3 Gen 2.0 with the MDEDR puffing topography device connected with data recording *ad libitum* for 6 minutes (\pm 30 seconds).

Subjects will complete questionnaires about product evaluation, craving and liking assessments.

The start of product use of the 6 minutes *ad libitum* use period will be defined as T_0 . T_0 on Day 1 to Day 3 should be at approximately the same time in the morning, within a window of \pm 20 minutes. Venous blood samples will be obtained according to the standard operating procedures (SOPs) at the investigational site.

On Day 1, 15 blood samples will be collected for determination of nicotine concentration at the following time points in relation to T_0 with a time window as indicated in brackets:

Prior to T_0 :

- T_{-1} : 5 minutes (\pm 1 minute)

After T_0 :

- T_1 after 1 minute (\pm 30 seconds)
- T_2 after 2 minutes (\pm 1 minute)
- T_3 after 4 minutes (\pm 1 minute)
- T_4 after 6 minutes (\pm 1 minute)
- T_5 after 8 minutes (\pm 1 minute)
- T_6 after 10 minutes (\pm 1 minute)
- T_7 after 12 minutes (\pm 1 minute)
- T_8 after 15 minutes (\pm 2 minutes)
- T_9 after 30 minutes (\pm 2 minutes)
- T_{10} after 1 hour (\pm 5 minutes)
- T_{11} after 2 hours (\pm 5 minutes)
- T_{12} after 4 hours (\pm 5 minutes)

Philip Morris Products S.A.
 P4M3 Gen 2.0, P4-PK-04-US
 [REDACTED] Statistical Analysis Plan Number CA34617

- T13 after 10 hours (\pm 5 minutes)
- T14 after 24 hours (\pm 10 minutes) (Day 1 and Day 2 only)

On Day 2, 14 blood samples will be collected for determination of nicotine PK after allocated product use at the same time points, except time point T-1. The sample T14 after T0 on Day 1 will also be used to determine the nicotine baseline concentration prior to T0 on Day 2 and similarly, T14 after T0 on Day 2 for nicotine baseline concentration prior to T0 on Day 3.

On Day 3, 13 blood samples will be collected for determination of nicotine PK after allocated product use. The sample T14 after T0 on Day 3 will not be collected.

On Day 1 to Day 3, subjective effects of liking and craving will be assessed using a VAS (100 mm going from “strong disliking” to “strong liking” for VAS liking, and from “no craving” to “strong craving” for VAS craving) at the following time points in relation to T₀:

Prior to T₀ (for VAS craving assessment only)

- T-15: within 15 minutes prior to T₀

After T₀: (for VAS craving and VAS liking assessment) with a time window as indicated in brackets

- T1 after 4 minutes (\pm 1 minute)
- T2 after 10 minutes (\pm 1 minute)
- T3 after 15 minutes (\pm 1 minute)
- T4 after 30 minutes (\pm 2 minutes)
- T5 after 1 hour (\pm 5 minutes)
- T6 after 2 hours (\pm 5 minutes)
- T7 after 4 hours (\pm 5 minutes)
- T8 after 10 hours (\pm 5 minutes)

Additional subjective effects will be assessed on Day 1 to Day 3 by the ABOUT-Product experience questionnaire administered within 1 to 2 hours after T₀.

On Day 2, additional blood samples will be taken for determination of the nicotine concentration to evaluate terminal elimination half-life (t_{1/2z}) in relation to T₀ from Day 2 at the following time points with a time window as indicated in brackets:

- T1z after 8 hours (\pm 5 minutes) after T₀ from Day 2
- T2z after 12 hours (\pm 5 minutes) after T₀ from Day 2
- T3z after 16 hours (\pm 10 minutes) after T₀ from Day 2
- T4z after 20 hours (\pm 10 minutes) after T₀ from Day 2

After enrollment at Day -1, the use of any other tobacco and nicotine containing products different from the product assigned for 6 minutes *ad libitum* use on Day 1 to Day 3, will not be allowed. Use of tobacco and nicotine containing products will not be restricted after the subject has been discharged from the investigational site on Day 3.

After discharge at Day 3, the subjects will enter a 3-day Safety Follow-Up Period (FU Period) during which AE/SAEs reported by the subjects will be collected and the follow-up of AEs/SAEs ongoing at discharge will be conducted by the investigational site.

Philip Morris Products S.A.
P4M3 Gen 2.0, P4-PK-04-US

██████████ Statistical Analysis Plan Number CA34617

Subjects who will be discontinued from the study before enrollment will be replaced. After enrollment but before randomization, subjects who will be discontinued from the study will enter the 3-day Safety Follow-Up Period and will be replaced. However, subjects that are discontinued after randomization will not be replaced.

3.2 Selection of Study Population

Thirty-six (36) subjects will be randomized to one of six possible product use sequences at Day 1.

The study population will be stratified by sex. Each sex will have a quota applied to ensure they represent at least 40% of the total randomized subjects.

In addition, at least 15% subjects of Black, Asian, American Indian or Alaska native, Native Hawaiian, other Pacific Islander race will be randomized to account for the US American smoking population. The randomization of subjects by ethnicity will not be enforced by stratification.

3.2.1 Inclusion Criteria

Subjects who meet all the following inclusion criteria can be enrolled into the study:

Inclusion Criteria	Screening	Admission (Day -1)
1. Subject has signed the ICF and is able to understand the information provided in the ICF.	X	
2. Smoking male or female aged between 24 and 65 years old.	X	
3. Subject has smoked continuously for at least the last 3 years prior to the Screening visit.	X	
4. Subjects has smoked ≥ 10 commercially available cigarettes per day for 4 weeks prior to Screening Visit and Admission. Smoking status will be verified based on a urinary cotinine test (cotinine ≥ 200 ng/mL).	X	X
5. Subject does not plan to quit smoking cigarettes or using other nicotine or tobacco-containing products in the next 3 months.	X	X
6. Smoking, healthy subject as judged by the Investigator or designee based on available assessments from the Screening period (e.g., safety laboratory, spirometry, vital signs, physical examination, ECG, and medical history).	X	

Philip Morris Products S.A.
 P4M3 Gen 2.0, P4-PK-04-US
 [REDACTED] Statistical Analysis Plan Number CA34617

Inclusion Criteria	Screening	Admission (Day -1)
7. Subject is available for the entire study period and willing to comply with study procedures, including product use assignments, and periods of abstinence from any nicotine/tobacco containing products.	X	X

3.2.2 Exclusion Criteria

Subjects who meet any of the following exclusion criteria must not be enrolled into the study:

Exclusion Criteria	Screening	Admission (Day -1)
1. As per the Investigator's judgment, the subject cannot participate in the study for any reason other than medical (e.g., psychological, social reason).	X	
2. Subject is legally incompetent, or physically or mentally incapable of giving consent (e.g., emergency situation, under guardianship, prisoners, or subjects who are involuntarily incarcerated).	X	
3. Subject has a clinically relevant disease which requires medication (including but not limited to gastrointestinal, renal, hepatic, neurological, hematological, endocrine, oncological, urological, immunological, pulmonary, and cardiovascular disease) or any other medical condition (including safety laboratory as per CTCAE), which as per the judgment of the Investigator would jeopardize the safety of the subject.	X	
4. As per the Investigator's judgment, the subject has medical conditions which require or will require in the course of the study, a medical intervention (e.g., start of treatment, surgery, hospitalization) which may interfere with the study participation and/or study results.	X	
5. Subject has donated or received whole blood or blood products within 3 months prior to Screening Visit.	X	
6. BMI < 18.5 kg/m ² or > 35.0 kg/m ² .	X	

Philip Morris Products S.A.
 P4M3 Gen 2.0, P4-PK-04-US
 [REDACTED] Statistical Analysis Plan Number CA34617

Exclusion Criteria	Screening	Admission (Day -1)
7. Subject has received medication within 14 days or within 5 half-lives of the drug prior to Admission, whichever is longer, which has an impact on CYP2A6 activity.		X
8. Subject has a positive serology test for HIV 1/2, Hepatitis B, or Hepatitis C or SARS-CoV-2.	X	
9. Subject has a history of alcohol abuse that could interfere with the subject's participation in study.	X	
10. Subject has a positive urine drug test. If positive for cannabinoids, inclusion will be at the discretion of the Investigator.	X	X
11. Subject has a positive alcohol breath test.	X	X
12. Subject or one of their family members ^a is a current or former employee of the tobacco industry.	X	
13. Subject or one of their family members ^a is employee of the investigational site or of any other parties involved in the study.	X	
14. Subject has participated in another clinical study within 3 months prior to the Screening Visit.	X	
15. Subject has been previously screened or enrolled in this study.	X	
16. For women only: subject is pregnant (does not have negative pregnancy tests at Screening Visit and at Admission) or is breastfeeding.	X	X
17. For women of childbearing potential only ^b : subject does not agree to use an acceptable method of effective contraception ^c .	X	X
18. Use of estrogen-containing hormonal contraception or hormone replacement therapy.	X	X

a. As defined by FDA guidance on Human Subject Protection (21 CFR 50.3(l), (m), 50.24(a)(6), (a)(7)(v), b): "Family member" means among other things "parent", "spouse", "brothers, sisters, and spouses of brothers and sisters" and "any individual related by affinity...whose close association with the subject is equivalent of a family relationship."

Philip Morris Products S.A.
P4M3 Gen 2.0, P4-PK-04-US

██████████ Statistical Analysis Plan Number CA34617

- b. Women who are not of childbearing potential meet at least one of the following criteria:
 - Have undergone hysterectomy or bilateral tubal ligation,
 - Have primary ovarian insufficiency, or
 - Are medically confirmed to be post-menopausal (cessation of regular menses for at least 12 consecutive months with no alternative pathological or physiological cause).
- c. Intrauterine device, intrauterine system, barrier methods of contraception (condoms, occlusive caps) with spermicidal foam/gel/film/suppository, hormonal contraception, vasectomized partner(s), or true abstinence (periodic abstinence and withdrawal are not effective methods) from Screening until the end of the Safety Follow-Up Period.

3.3 Discontinuation of Subjects from the Study

Discontinued subjects will include both, subjects who withdraw from the study (subject's decision) and subjects who are discontinued from the study by the decision of the Investigator. A subject can only be discontinued from the study after enrollment.

Subjects will be informed that they are free to withdraw from the study at any time. Subjects will be questioned for the reason for withdrawal from the study, although they are not obliged to disclose it. If a subject withdraws from the study, he/she will be asked to confirm that he/she agrees to undertake the early termination procedures for safety assessments, and this information will be fully documented by the Investigator.

The subject will be informed that if he/she withdraws from the study, the data collected until the point of withdrawal will be maintained as part of the study data and the samples collected prior to withdrawal will be analyzed, unless the subject disagrees in writing.

When a subject is discontinued from the study, all early termination procedures (study protocol Section 9.7) will be performed unless the subject refuses to perform the assessments or the procedures have already been performed during the study day. Early termination procedures are to be performed only for subjects who have been exposed to P4M3 Gen 2.0. After the date of termination, the subject will enter into the 3-day Safety Follow-Up Period. This applies to all subjects independent of the reason of discontinuation (for example, withdrawal of consent, or at the Investigator's decision, etc.).

Subjects must be discontinued from the study for any of the following reasons:

- Withdrawal of informed consent.
- Any AE/SAE or condition (including clinically significant changes in a laboratory parameter), which at the discretion of the Investigator is not compatible with the subject's continued participation in this study.
- Positive pregnancy test (study protocol Section 8.5).
- If the Sponsor decides to prematurely terminate the study, the subject will be promptly informed by the Investigator. The Investigator should report the fact and the reason in writing to the IRB.
- Discontinuation is considered to be in the best interest of the subject or the other subjects as judged by the Investigator.

Philip Morris Products S.A.
P4M3 Gen 2.0, P4-PK-04-US

██████████ Statistical Analysis Plan Number CA34617

- Subject is not willing and/or ready to use P4M3 Gen 2.0 after the product test at Admission (Day -1). In such a situation, the subject will be discontinued after the product test and will enter the 3-day Safety Follow-up.
- Subject uses any tobacco or nicotine-containing product different from the assigned product during confinement.

Subjects may be discontinued from the study for the following reasons:

- Non-compliance to the study procedures based on the judgment of the Investigator.
- A sufficient number of subjects are already randomized to the study sequences (study protocol Section 5.2). In this case, additional subjects (alternates) will be discontinued prior to randomization.
- Violations of eligibility criteria have been determined (study protocol Section 5.4).

Subjects who will be discontinued from the study before enrollment will be replaced. After enrollment but before randomization, subjects who will be discontinued from the study will enter the 3-day Safety Follow-Up Period and will be replaced. However, subjects discontinued after randomization will not be replaced.

4. ANALYSIS POPULATIONS

4.1 Analysis Populations

Populations will be described on the screened population.

Demographics, baseline characteristics, pharmacokinetics endpoints, pharmacodynamics endpoints, human puffing topography parameters, amount of nicotine delivered, will be analyzed using the PK population.

Safety will be analyzed using the safety population.

4.1.1 Screened Population

The screened population consists of all subjects who underwent screening.

4.1.2 Safety Population

The safety population is a subset of the screened population and consists of all subjects who give informed consent, have at least one exposure to P4M3 Gen 2.0, including the product test at Admission (Day -1), and have at least one safety assessment.

4.1.3 Pharmacokinetic Population

The Pharmacokinetic (PK) Population is a subset of the safety population and consists of all randomized subjects for whom at least one nicotine PK parameter can be derived. Only subjects without major protocol deviations, as defined in [Section 4.2.1.1](#), which have an impact on evaluability of the main objective will be included in the PK population.

4.2 Protocol Deviations

Protocol deviations are defined as any departure from the procedures defined in the study protocol, including, but not limited to, any violation of inclusion/exclusion criteria, mis-randomization, use of any nicotine or tobacco-containing product other than the assigned product during the exposure period, assessments not performed or performed outside the scheduled time windows, or use of medications that are known to affect study endpoints.

4.2.1 Data Collection

Protocol deviations will be entered into the clinical trial management system (CTMS) or other approved format. The data collected in the CRF may be used to assess protocol deviations from the data programmatically. Protocol deviations will be reconciled and categorized prior to locking the clinical database as described in the data management plan (DMP).

All deviations will be reviewed to determine their impact when subjects are assigned to analysis populations. Each deviation will be classified as major or minor.

4.2.1.1 Major Protocol Deviations

Subjects with major protocol deviations will be identified (at a population level) to determine whether they will be excluded from any of the analysis populations.

Major deviations will include but are not limited to the deviations presented in [Table 1](#).

Table 1 - Definition of Major Protocol Deviation Categories

Sub-Category	Description
Violation	Violation of inclusion/exclusion criteria
Mis-randomization	Violation of the product allocation process, including but not limited to the misclassification of subject's sex at randomization and incorrect product administered according to randomized sequence
Mis-use of product	Use of any nicotine or tobacco-containing product other than the assigned product during the exposure period, or use of any nicotine tobacco-containing product during at least 10 hours of abstinence from any nicotine/tobacco containing products (nicotine wash-out). Product use not compliant with planned regimen
Concomitant medications	Use of any drugs which are known to affect CYP2A6 activity

Among the eligibility criteria, violations of inclusion criteria 1, 2, 3, 4 and 7, or of the exclusion criteria 2 and 15 will be considered as impacting the evaluability or integrity of the primary objective. Other major protocol deviations will be assessed for their impact on the evaluability of the primary objective during the pre-analysis data review meeting.

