The PK of plasma nicotine presents a biphasic profile, with a typical rapid initial disposition half-life ($t_{1/2a}$) of 1.35 hours, followed by a slower terminal elimination half-life ($t_{1/2z}$) of hours [15]. To ensure a complete nicotine washout between each product use, 3 days without product use (cigarette or P4M3 Gen 2.0) would have been required ($\sim 5 \times$ terminal elimination $t_{1/2z}$). Based on nicotine population PK modeling, it was estimated that nicotine enters in the terminal elimination phase with concentrations decreasing with a terminal elimination rate constant (λ_z) 8 to 10 hours post administration. As a consequence, a minimum of 12 hours has been established in this study design prior to T_0 on Day 1 and approximately 24 hours prior to T_0 on Day 2 and Day 3. Background-concentration correction will be applied to adjust for carry-over effects with adjustment of baseline values to the estimated $t_{1/2z}$ (or λ_z) which will be derived from additional blood sampling on Day 2 and Day 3 for each subject.

The use of estrogen contraceptive is known to accelerate nicotine clearance by 20% to 30% compared to women who do not take estrogen contraceptive [16]. Therefore, for the purpose of this study, use of hormonal contraception containing estrogens is prohibited. This also applies to hormone replacement therapy.

The activity of CYP2A6 will be measured as this enzyme drives the metabolism of nicotine into cotinine and subsequent metabolites. Nicotine metabolism by CYP2A6 varies between individuals of the same ethnicity/race and across ethnicity/race due to genetic variations. These genetic differences could be associated with reduced/increased nicotine metabolism [14].

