6.2.2 Exposure Period (Day 1 and Day 3)

On Day 1 to Day 3, after at least 12 hours of abstinence from any tobacco/nicotine containing products, subjects will start using their allocated product *ad libitum* for 6 minutes ± 30 seconds (section 4.1).

For P4M3 Gen 2.0 use, subjects will be provided with a new P4M3 Gen 2.0 Cartridge (CA35 or CM35 depending on product assignment) and a fully charged P4M3 Gen 2.0 Battery unit with the MDEDR puffing topography device connected.

For cigarette smoking, subjects will smoke one cigarette *ad libitum* for 6 minutes ± 30 seconds.

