6.6 Restrictions

6.6.1 Smoking Restrictions

During the Screening period, subjects will be allowed to use any nicotine/tobacco-containing products according to their usual habits except during the procedures of the Screening Visit (section 9.1). Spirometry assessments at Screening and at Day -1 will be performed 1 hour after stopping smoking (section 9.1 and 9.2).

From Admission (Day -1) to Discharge (Day 3) or early termination, use of any nicotine/tobacco containing products, except use as per study design of the allocated product will not be permitted.

A nicotine washout period of at least 12 hours should be respected before product use at Day 1 to Day 3.

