11. SUMMARY OF CHANGES FROM PROTOCOL-PLANNED ANALYSIS

Per protocol, demographics, baseline characteristics, pharmacokinetics endpoints, pharmacodynamics endpoints, human puffing topography parameters, amount of nicotine

Philip Morris Products S.A.
P4M3 Gen 2.0, P4-PK-04-US

██████████ Statistical Analysis Plan Number CA34617

delivered, will be analyzed using the randomized and PK population. They will be analyzed only in the PK population. The randomized population will not be defined.

Where comparisons between CA35 and Cigarettes, and between CM35 and Cigarettes, are performed, the comparison between CA35 and CM35 will be performed additionally.

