Program: /CAXXXXX/ECR/sas_prg/stsas/lis_PROGRAMNAME.sas DDMMYYYY HH:MM Status: DRAFT (Page X of Y)

Philip Morris Products S.A.
P4M3 Gen 2.0, P4-PK-04-US

████████ Statistical Analysis Plan Number CA34617

Listing 15.3.2.2 P4M3 Gen 2.0 Product Test (Day -1) (Safety Population)

Subject Number	Study Period	Did Subject Participate in Product test?	If No, Reason For Not Done	Date of Test	Start Time	End Time
X	XXX	XXX		DDMMYYYY	HH:MM	HH:MM

Program: /CAXXXXX/ECR/sas_prg/stsas/lis_PROGRAMNAME.sas DDMMYYYY HH:MM Status: DRAFT (Page X of Y)

Philip Morris Products S.A.
P4M3 Gen 2.0, P4-PK-04-US

████████ Statistical Analysis Plan Number CA34617

Listing 15.3.2.3 Randomization (Safety Population)

Subject Number	Study Period	Was The Subject Randomized?	Date	Randomization Sequence
X	Day-1	XXX	DDMMYYYY	XXXX-XXXX-XXXX

CA35 = P4M3 Gen 2.0 Classic Auburn

CM35 = P4M3 Gen 2.0 Classic Menthol

Program: /CAXXXX/ECR/sas_prg/stsas/lis_PROGRAMNAME.sas DDMMYYYY HH:MM Status: DRAFT (Page X of Y)

Philip Morris Products S.A.
P4M3 Gen 2.0, P4-PK-04-US

████████ Statistical Analysis Plan Number CA34617

Listing 15.3.2.4 Product Use (Safety Population)

Subject Number	Study Day	Was Product Dispensed?	If No, Reason for Not Done	Was Used Product Collected?	If No, Reason for Not Done	Product Abstain?*	P4M3 Dispensed ID	Product Date	Batch Number	Start Time	End Time
X	1	XXX		XXX		XXX	XXX	XXXX DDMMYYYY XXXXXXXX		HH:MM:SS	HH:MM:SS

CA35 = P4M3 Gen 2.0 Classic Auburn

CM35 = P4M3 Gen 2.0 Classic Menthol

* Did subject abstain from any nicotine/tobacco containing products at least 12 hours prior to product use?

Program: /CAXXXXX/ECR/sas_prg/stsas/lis_PROGRAMNAME.sas DDMMYYYY HH:MM Status: DRAFT (Page X of Y)

Philip Morris Products S.A.
P4M3 Gen 2.0, P4-PK-04-US

████████ Statistical Analysis Plan Number CA34617

Listing 15.3.2.5 Product Use - Cartridge Weight and Amount of Nicotine Delivered (Safety Population)

Subject Number	Dispense Date	Product Dispensed	P4M3 ID	Pre-product Use Cartridge Weight (mg)	Post-product Use Cartridge Weight (mg)	Difference (mg)	Amount of Nicotine Delivered (mg)
X	DDMMYYYY	X	XXX	XXXX	XXXX	XXXX	XXXX

CA35 = P4M3 Gen 2.0 Classic Auburn

CM35 = P4M3 Gen 2.0 Classic Menthol

The amount of nicotine delivery from P4M3 Gen 2.0 is calculated by dividing the difference in the cartridge weight [mg] by the specific density of the e-liquid [1129.2 mg/mL] multiplied by the nicotine concentration [39.5 mg/mL].

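### SAP Table 1 puts the nicotine wash-out at 10 h in its major-deviation clause where the protocol and the rest of the SAP require 12 h; Table 3 and one table shell need small companion corrections

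*SAP*

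**What the plan says.** **Wash-out.** Table 1 in SAP 4.2.1.1 treats as major "use of any nicotine tobacco-containing product during at least 10 hours of abstinence" and labels that period the nicotine wash-out. Elsewhere the figure is 12 h:

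- Protocol 4.2, on the interval before T0 on Day 1: "a minimum of 12 hours has been established in this study design".
- Protocol 6.2.2: "On Day 1 to Day 3, after at least 12 hours of abstinence from any tobacco/nicotine containing products".
- Protocol 6.6.1: "A nicotine washout period of at least 12 hours should be respected before product use at Day 1 to Day 3".
- SAP 3.1, repeating Protocol 4.1: "after at least 12 hours of abstinence from any nicotine/tobacco containing products (nicotine wash-out".
- SAP Listing 15.3.2.4, footnote to the abstinence column: "Did subject abstain from any nicotine/tobacco containing products at least 12 hours prior to product use".

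SAP 4.1.3 refers to Section 4.2.1.1 for the major deviations that can remove a subject from the PK population.

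**Assessment windows.** SAP Table 3 gives ECG windows for Days 1, 2 and 3 and for Day 4, and a vital-sign row for Day 4. Protocol Appendix A and SAP 10.10 schedule ECGs at Screening, Day -1 and Day 3 (or early termination). SAP 10.9 ends vital signs at Day 3. Protocol Table 10 lists vital signs twice on Day 3: before T0 and again among the discharge procedures.

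**Deviation table.** The footnote of the Table 15.2.1.2.1 shell makes the total number of deviations the base for percentages. The first row of that shell is a count and percentage of subjects with at least one deviation.

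**The concern.** The major-deviation list is operative text, because it supplies the cases that are reviewed for the PK population. Every other statement of the wash-out minimum is 12 h, so a threshold of 10 h leaves a two-hour band in which a subject breaks the protocol, and is flagged in Listing 15.3.2.4, without meeting the explicit wash-out clause of Table 1. The data review meeting should not have to settle which number was meant after the data are in.

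The two companion items are of the same kind. Table 2 refers to the section containing Table 3 for time deviations, so Table 3 should list only scheduled assessments. SAP 14.1.5 makes footnotes the place where denominators are defined, so a wrong footnote can produce a wrong percentage.

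**Working it through.** **1. Which number is the rule.** Table 1 stands alone at 10 h against Protocol 4.1, 4.2, 6.2.2 and 6.6.1, SAP 3.1 and Listing 15.3.2.4 at 12 h. SAP Section 11 declares two changes from the protocol: the populations ("They will be analyzed only in the PK population. The randomized population will not be defined") and an added comparison of CA35 with CM35. The wash-out is not mentioned.

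**2. When the two hours can matter.** Protocol 4.2 puts about 24 h between product uses before Days 2 and 3, so only Day 1 is exposed. The realistic route is a late Day -1 product test. T0 is in the morning, so a test 10 to 12 h earlier would fall in the previous evening (for an assumed T0 of 08:00, between 20:00 and 22:00). That is unlikely: Protocol Table 7 puts the test after the CYP2A6 sample, and Appendix A footnote g puts the Day -1 safety bloods in the morning. Use of a non-assigned product during confinement already requires discontinuation (Protocol 5.2, SAP 3.3).

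**3. Size of the effect on baseline nicotine.** The half-life value is missing from the text available. Protocol 4.2 says that for complete wash-out "3 days without product use (cigarette or P4M3 Gen 2.0) would have been required" and equates this with about 5 terminal half-lives:

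- Implied half-life = 72 h / 5 = 14.4 h.
- Residual after 10 h relative to 12 h = 2^(2/14.4) = 1.10.
- For assumed half-lives of 20 h and 8 h: 2^(2/20) = 1.07 and 2^(2/8) = 1.19.

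The ratio needs both times to lie in the terminal phase, which agrees with Protocol 4.2 (onset 8 to 10 h after use).

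The sensitivity analysis in SAP 6.5.2 drops a subject-day whose baseline exceeds 5% of its uncorrected maximum. Suppose the whole baseline came from that one use and the maximum stayed fixed. Then the 12 h baseline that reaches 5% at 10 h is 5% / 1.101 = 4.54%. The two hours could move a subject-day across the trigger only from a starting value of about 4.5% to 5%.

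**4. Table 3.** Unscheduled ECG days: 1, 2 and 4, three entries. The Day 4 ECG window is set relative to T0, but product use ends on Day 3, so there is no T0 on Day 4. The Day 4 vital-sign row is a fourth entry without a scheduled visit. If it were simply deleted, Day 3 would keep only a before-T0 window and the discharge reading in Protocol Table 10 would have no row.

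**5. Deviation shell.** If the footnote is followed for the subject row, the printed percentage = affected subjects / total deviations = 1 / (mean deviations per affected subject), whatever share of subjects is affected. Assumed extremes, with 36 subjects in the column:

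| Case | Correct | Printed |
|---|---|---|
| 1 subject, 1 deviation | 1/36 = 2.8% | 1/1 = 100% |
| 36 subjects, 3 deviations each | 36/36 = 100% | 36/108 = 33.3% |

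**The case against.** The best defence is that a grading cut-off need not equal the conduct rule. Protocol 12.3.4 leaves the definition of major deviations to the SAP, so Section 11 need not list the 10 h figure as a change, and its silence is weak evidence of error. Protocol 4.2 places the start of the terminal phase at 8 to 10 h, so the background correction is about as applicable at 10 h as at 12 h. SAP Table 2 grades procedural breaches without effect on evaluability as minor. A deliberate tolerance is therefore conceivable. But the SAP does not state one, and Table 1 uses the term that SAP 3.1 applies to the 12 h period. If a tolerance was meant, it has to be written down. Either way the line needs an edit.

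A reader might infer that the PK population will be built on the wrong wash-out rule. The documents do not support that. The last sentence of the same Table 1 cell makes use that departs from the planned regimen a major deviation, and the list is explicitly open-ended. SAP 4.2 still counts any departure from the protocol as a deviation. SAP 4.1.3 excludes only for major deviations that affect evaluability of the main objective. Apart from the named eligibility criteria, that is judged at the pre-analysis data review meeting. The 10 h figure by itself neither admits nor removes anyone.

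On the companion items, SAP 14 says that shells may change and SAP 4.2.2 already asks for the percentage of subjects, so a careful programmer would probably get the table right.

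**Conclusion.** The 10 h figure is wrong as written, and the point is minor. It rests on comparing the texts, which needs no assumption. The size estimate is illustrative only: it uses a half-life back-calculated from rounded figures and attributes the whole baseline to one late use. Participants smoke at least 10 cigarettes a day up to Admission, so earlier smoking also contributes to the Day 1 baseline and would dilute the effect of the two hours. The documents do not show how many subjects, if any, would fall in the 10 to 12 h band.

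It would go too far to conclude that the nicotine exposure ratios are at risk. Background correction and the 5% sensitivity analysis both act on the Day 1 baseline, and nothing in the documents points to a changed estimate. Nor do the Table 3 entries show that false deviations will be counted, or the shell footnote that a wrong percentage will be reported. These two items affect no endpoint and no analysis population.

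**What to change.** - **Table 1:** change 10 h to 12 h. If a tolerance was intended, state it and give the reason.
- **Table 3:** delete the ECG entries for Days 1, 2 and 4, and keep Day 3 at 60 ± 10 min after T0. Relabel the Day 4 vital-sign row as Day 3 discharge. Check this against Protocol Table 10 first, because Protocol 7.4.5 mentions only the readings before T0 on Days 1 to 3.
- **Table 15.2.1.2.1 shell:** use the number of subjects in the column as denominator for the row of subjects with at least one deviation, and keep the number of deviations for the deviation rows.

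The cost is wording edits to two SAP tables and one shell footnote before database lock. No sample size, model or endpoint changes.
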